**Table 3. Grading Scale for Diaper Dermatitis**

Parameters	Normal	Slight	Mild	Moderate	Severe
	0	1	2	3	4
Diaper dermatitis	No clinical sign	Faint to definite pinkness over small area, may be a single raised bump (papule), may be slight dryness	Faint to definite pinkness over small area, definite redness over a very small area, scattered raised bumps (papule),	Faint to definite pinkness in a larger area, definite redness over a small area, very intense redness in a very small	Definite redness in a larger area, very intense redness in a very small area, single to several areas of raised bumps (papules), presence of

			moderate dryness	area, scattered raised bumps (papules), moderate dryness	erosions, may have slight peeling, may have swelling (edema), may have scaling
--	--	--	------------------	--	--

**Figure 2. Visualization Corresponding to the Grading Scale for Diaper Dermatitis**

## 10.2 Digital Photography

With subject's parent/legal guardian's consent, photographs will be taken prior to treatments with study product and at every follow-up visit in order to document treatment effect. Site personnel will be thoroughly trained in the photographic equipment and techniques before study start. All photographs will be taken zoomed into the area to the extent that no body part is distinguishable.

Camera equipment will be provided by the Sponsor or their designee and standardized photographs should be achieved. Further details regarding photography procedure will be specified in a separate user guide.

## 10.3 Self-Assessment Questionnaire

Subjects' parent/legal guardians will be asked about their perception and satisfaction with the study product using a self-assessment questionnaire after the first application and at each visit (see Appendix II).

## 11. SAFETY ASSESSMENTS

Safety assessments for this study include an evaluation and an interview of the subjects' parent/legal guardians at each visit to obtain information about any medical occurrence that meets the definition of an AE, and a subject diary. In addition, Investigator will perform tolerability assessment to grade the degree of irritation.

Protocol GLI.04.US.SL.023

CONFIDENTIAL

### 11.1 Assessment of AEs by Direct Questioning to Subject

Each subject's parent/legal guardian should be questioned about AEs at each visit following treatment. Definition and reporting requirements are found in Section 13.

### 11.2 Subject Diary

A subject diary will be dispensed to all subjects' parent/legal guardians for daily completion. The subject's parent/legal guardian will be specifically instructed to record presence of any symptoms that occur in the product application areas. Diary data will be counted and displayed separately from other AE data.

### 11.3 Tolerability Assessment

Tolerability assessments will be performed by Investigator at each visit prior to treatments with study product and at every follow-up visit. Investigator will grade the degree of irritation parameters that they observe in subject based on a 4-point analog scale, described in [Table 4](#) (with half-point scores used as necessary to better describe the clinical condition).

**Table 4. Tolerability Assessment Scale**

Parameters	Score 0	Score 1	Score 2	Score 3
Dryness	None	Mild	Moderate	Severe
Peeling	None	Mild	Moderate	Severe
Edema	None	Mild	Moderate	Severe

## 12. STATISTICAL ANALYSIS

### 12.1 General

All study data will be listed in subject data listings.

All statistical analyses, including summary tables and data listings, will be performed. Confidence intervals will be two-sided and constructed at a confidence level of 95%. Statistical tests will be performed at a significance level of 5%, and  $p$  values will be two-sided.

All endpoints will be summarized descriptively including N, mean, median, standard deviation, minimum and maximum values, for the observed value as well as the change from baseline. Categorical endpoints will be presented in frequency tables with number and percentage of observations for each level.

### 12.2 Analysis Population

The following populations will be defined:

Intention-to-treat (ITT)	Includes all subjects who receive a test product. Subjects are analyzed based on the as treated principle.
--------------------------	--

Protocol Version: 01

This document contains confidential, proprietary information.

Protocol GLI.04.US.SL.023

CONFIDENTIAL

Per protocol (PP) Includes all subjects in ITT who complete the study after pre-conditioning visit without any deviations that are considered to have substantial impact on the primary effectiveness outcome.

ITT is the primary population for all effectiveness and safety analyses. The primary effectiveness analysis will be repeated using the PP analysis set if there is at least a 10% difference in the number of subjects between the PP and ITT sets.

### 12.3 Demographics and Subject Characteristics

Demographic endpoints and subject characteristics will be presented based on the ITT analysis set using descriptive statistics, as appropriate.

### 12.4 Statistical Analysis Plan

Mean of the change from Baseline will be estimated at applicable post-Baseline timepoint. The null hypothesis, that the mean change from Baseline is zero, will be tested using methods described in [Table 5. Statistical Analysis Plan](#).

The following will be calculated and reported for each parameter at applicable post-Baseline timepoint(s):

$$\text{Percent mean change from baseline} = \frac{(\text{visit mean score} - \text{baseline mean score})}{\text{baseline mean score}} \times 100$$

$$\text{Percent of subjects improved/worsened} = \frac{(\text{number of subjects improved/worsened from baseline})}{\text{total number of subjects}} \times 100$$

**Table 5. Statistical Analysis Plan**

Evaluation	Change from Baseline	Notes/Interpretation
Efficacy Grading 

Skin smoothness (tactile)

Skin texture

Diaper dermatitis

	Paired t-test; If normality fails, a Wilcoxon signed-rank test will be used.	A decrease in scores indicates an improvement
Tolerability Grading 

Dryness

Peeling

Edema

	Paired t-test; If normality fails, a Wilcoxon signed-rank test will be used.	A decrease in scores or lack of significant increase indicates tolerability/safety of the treatment product
Self-Assessment Questionnaire	N/A	Percentage of favorable and unfavorable responses will be provided for each question

Questionnaires will be tabulated; and the frequency and percentage of all response options will be reported for each question and time point. For questionnaire inquiries without baseline response data, a binomial (sign) test will be performed to test if the proportion of the combined designated favorable responses is equal to the combined designated unfavorable responses for each applicable question. A higher percentage of favorable responses with a significant *p* value indicates positive subject perceptions of the study treatment.

Protocol Version: 01

This document contains confidential, proprietary information.

Protocol GLI.04.US.SL.023

CONFIDENTIAL

A more appropriate analysis may be performed, which will be recorded in biostatistics note to file and/or in the study report.

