### 3. BACKGROUND AND RATIONALE

Diaper dermatitis is the most common skin disorder seen in young infants and affects those using diapers. Increased moisture resulting from wearing diapers leads to increased friction and maceration, making the skin more susceptible to damage. Infants with diaper dermatitis can present with erythema, edema, scaling, peeling, papules and dryness, and diagnosis is based on skin findings. Management of diaper dermatitis must both heal damaged skin and prevent rash recurrence. The use of topical emollients is recommended to improve skin barrier function, prevent over-hydration, and provide a barrier between the skin and the diaper, limiting contact with the skin. It is recommended to apply emollients with every diaper change.

Cetaphil® Healing Ointment (Galderma, Dallas, TX) is an Over-the-Counter (OTC) skin protectant that contains 71.5% petrolatum, shea butter to soften, smooth and hydrate, as well as vitamin E to help support moisture barrier function. The Healing Ointment has been clinically proven to hydrate the skin's natural barrier for 48 hours while quickly protecting and healing dry, cracked, irritated skin for visible improvement in 1 week. The product is also hypoallergenic, non-comedogenic, gentle on sensitive skin and accepted by the National Eczema Association. These beneficial properties make Cetaphil® Healing Ointment an ideal candidate as a treatment for diaper rash in infants. This study is to investigate safety and efficacy of Cetaphil® Healing Ointment on infants with diaper rash.

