#### 4.2 Clinical Hypothesis

The Sponsor's test material will produce a statistically significant improvement in clinical grading of efficacy parameter scores over the course of 3 weeks of use when compared with baseline scores/values. Additionally, the Sponsor's test material will be well tolerated by the subjects, with no statistically significant increases in scores for tolerability/safety parameters at any study time point when compared with baseline scores. Furthermore, the Sponsor's test material will be well perceived by the subjects' parent/legal guardians according to a self-assessment questionnaire at day 1, week 1 and week 3, with a statistically significant proportion of favorable responses compared to unfavorable responses.

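### Table 5 and Section 4.2 read a non-significant mean change, or any fall in the mean, as proof of tolerability, with no margin and at most 30 completers

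*Combined protocol and SAP*

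**What the plan says.** The combined protocol and SAP sets the tolerability criterion in two places. The interpretation column of Table 5 (Section 12.4), for dryness, peeling and edema, reads: "A decrease in scores or lack of significant increase indicates tolerability/safety of the treatment product". Section 4.2 makes the product well tolerated if there are "no statistically significant increases in scores for tolerability/safety parameters at any study time point when compared with baseline scores".

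The test behind the criterion is one of difference. Section 12.4 says: "The null hypothesis, that the mean change from Baseline is zero, will be tested using methods described in" Table 5, and the method given there is "Paired t-test; If normality fails, a Wilcoxon signed-rank test will be used". Section 12.1 sets a 5% level with two-sided p values. Section 6.1 caps the study at 30 completers. No margin, acceptable worsening rate, power or standard deviation is given anywhere. The plan does not say how normality is judged, or which form of the Wilcoxon test (exact or approximate, treatment of zeros and ties) applies.

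Section 11.3 and Table 4 grade each sign from 0 to 3, with half points allowed. Section 3 lists the same signs as features of the rash itself: "Infants with diaper dermatitis can present with erythema, edema, scaling, peeling, papules and dryness".

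**The concern.** A test of zero mean change that fails to reject shows only that the data did not rule out zero. It does not show that worsening is small. Under this rule, the fewer infants are studied, the easier it is to conclude that the product is tolerated.

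The alternative route, a decrease in scores, needs no significance at all and has a second weakness. The criterion concerns the mean, so infants whose rash-related signs resolve can offset infants who get worse. A lower mean is therefore not evidence that individual infants tolerated the product.

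Safety is a stated objective (Synopsis and Section 4.1) and the subjects are infants. What is at stake is a written conclusion of good tolerability when a meaningful share of them worsened.

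**Working it through.** The plan gives no derivation of its sample size and no margin, so there is no figure of its own to reproduce. The check applies the Table 5 tests to constructed change scores.

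**Inputs.** n = 30 (Section 6.1, used as the analysed number); two-sided 5% (Section 12.1); paired t-test or Wilcoxon signed-rank (Table 5); grades 0 to 3 (Table 4). One sign, one visit.

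**A. k infants worsen by one grade, the other 30 − k unchanged.**

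- Paired t: the mean is k/n and the variance k(n − k)/[n(n − 1)], so t = √[k(n − 1)/(n − k)] on 29 df.
- Exact Wilcoxon, zeros dropped: all k non-zero changes are positive and tied, so p = 2 × 0.5^k.
- Asymptotic Wilcoxon, tie-corrected: z = √k.
- With continuity correction: z = √k − 2/[(k + 1)√k].

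| k (of 30) | t | p, t-test | p, exact | p, asymptotic | p, continuity-corrected |
|---|---|---|---|---|---|
| 3 (10%) | √(87/27) = 1.80 | 0.083 | 0.250 | 0.083 | 0.149 |
| 4 (13%) | √(116/26) = 2.11 | 0.043 | 0.125 | 0.046 | 0.072 |
| 5 (17%) | √(145/25) = 2.41 | 0.023 | 0.0625 | 0.025 | 0.037 |
| 6 (20%) | √(174/24) = 2.69 | 0.012 | 0.031 | 0.014 | 0.020 |

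Three pass under every version. Four pass under the exact and continuity-corrected Wilcoxon, five under the exact Wilcoxon only, and six under none. The limits of 3 and 5 are the same for n = 27 to 33 (3/33 = 9% up to 5/27 = 19%).

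**B. How often the rule would pass**, others unchanged, at an assumed true one-grade worsening rate. With X binomial(30, rate), the t-test passes when X ≤ 3 and the exact Wilcoxon when X ≤ 5. At 10% the chances are 65% and 93%; at 16.7% they are 24% and 62%.

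**C. Some infants worsen while others improve by one grade.**

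| Worsen | Improve by 1 | Mean change | p, t-test | p, exact | p, asymptotic | p, continuity-corrected |
|---|---|---|---|---|---|---|
| 6 by one grade | 1 | (6 − 1)/30 = 0.17 | 0.057 | 0.125 | 0.059 | 0.073 |
| 6 by two grades | 0 | 12/30 = 0.40 | 0.012 | 0.031 | 0.014 | 0.020 |
| 6 by two grades | 3 | (12 − 3)/30 = 0.30 | 0.083 | 0.031 | 0.043 | 0.0495 |
| 6 by two grades | 4 | (12 − 4)/30 = 0.27 | 0.133 | 0.090 | 0.066 | 0.074 |
| 6 by two grades | 18 | (12 − 18)/30 = −0.20 | 0.36 | 0.56 | 0.53 | 0.54 |

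Six infants worse by one grade pass every version once a single other infant improves. Six worse by two grades are flagged by every version if the rest are unchanged, and pass every version only when at least 4 others improve by one grade.

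**D. The decrease route.** If 10 worsen and 11 improve by one grade, the mean is (10 − 11)/30 = −0.03. That is a decrease, so Table 5 reads it as tolerability with a third of the infants worse.

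**E. Where offsetting is plausible.** Table 3 names dryness at the slight, mild and moderate grades, but peeling and edema only at the severe grade, which exclusion criterion 1 removes. On that scale, enrolled infants have dryness to lose but would mostly start near zero for peeling and edema.

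**F. What a direct estimate would show.** Exact (Clopper-Pearson) two-sided 95% limits: 0/30 has an upper limit of 11.6%; 3/30 gives 2.1% to 26.5%; 5/30 gives 5.6% to 34.7%; 6/30 has an upper limit of 38.6%.

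**The case against.** The strongest reply is that Table 5 is not the whole safety evaluation. Section 12.4 reports percent worsened for each parameter at each post-baseline time point. Section 11.2 has diary symptoms shown separately. Section 13 makes a clinically relevant untoward change in a graded parameter an adverse event whatever its cause. Section 13.1.2 records a local sign that leads to permanent discontinuation or corrective treatment as a related event. This stands: a reader might infer that reactions would go unseen, and the documents do not support that. But none of these outputs enters the criterion in Table 5 or Section 4.2, so the stated conclusion can still contradict them.

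Second, Section 4.2 asks for no significant increase at any time point. With three signs and two follow-up visits that is six chances to fail, and the figures above treat one. This makes the overall rule stricter than a single test, but each of the six still lacks a margin.

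Third, a reader might infer that 20% of infants could worsen by two grades and pass regardless. They could not: with the rest unchanged, every version flags it. Nor is 17% a general limit. Under the t-test, which the plan names first, the limit is 10%. With mostly zero changes normality would probably fail and the Wilcoxon would apply, but the plan does not name its version.

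Fourth, the general list in Section 3 might suggest offsetting for all three signs alike. Table 3 makes it most plausible for dryness; for peeling and edema the case is weaker, though not excluded.

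**Conclusion.** The criterion is wrong as written and should be fixed. Non-significance in about 30 infants, or any fall in the mean, is not evidence of tolerability when no margin or power has been set. With the other infants unchanged, the rule lets through 3 of 30 newly worse by one grade under any version of the test, and up to 5 of 30 under the exact Wilcoxon. With offsetting improvement it lets through 6 of 30: one improver suffices for one-grade worsening, and at least four are needed for two-grade worsening.

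These sizes assume 30 analysed infants, one sign at one visit, whole-grade changes and zeros dropped in the Wilcoxon test. The patterns of change are constructed for illustration; the documents give no expected distribution. The consequence is a possible false statement of good tolerability, not undetected reactions. That is why this is a defect to correct in the wording of the analysis rather than a failure of safety monitoring.

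**What to change.** Delete the interpretation sentence for tolerability from Table 5, and the matching no-significant-increase criterion from Section 4.2. Keep mean changes in dryness, peeling and edema as descriptive summaries.

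Base the tolerability statement on the number and percent of infants worsened from baseline, for each sign at each follow-up visit, with an exact two-sided 95% confidence interval. Section 12.4 already computes the percentage. Read it alongside the adverse events.

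A ceiling on the upper confidence limit, fixed before data are seen, is optional and for the sponsor to choose. It would be demanding at n = 30: a ceiling of 15% allows no worsened infant, 20% allows one and 25% allows two. Without a control arm, natural fluctuation of the rash and half-point shifts would count against the product.

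The cost is wording and a few intervals, with no new data. The claim becomes more modest, since even 0 of 30 worsened leaves an upper limit of 11.6%.

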### 13. ADVERSE EVENTS

Throughout the course of the study, all adverse events will be monitored and reported on an adverse event CRF/eCRF without omitting any requested and known information. When AEs occur, the main concern is the safety of the study subjects. At time of the informed consent signature, each subject must be given the name and phone number of investigational site personnel for reporting AEs and medical emergencies.

At each visit, after the subject has had the opportunity to spontaneously mention any problems, the Investigator should inquire about AEs by asking the standard questions:

- “Has your child had any health problems since your last study visit?”
- “Have there been any changes in the medicines your child take since your last study visit?”

AEs should be reported for any clinically relevant change, as determined by the Investigator, in concomitant medication(s) that is the result of an untoward (unfavorable and unintended) change from baseline in a subject’s medical health following exposure to the study treatment.

Changes from baseline in any protocol-specific parameter evaluated during the study are to be reviewed by the Investigator. In addition, the subject’s responses to any questionnaire utilized during the study are to be reviewed by the Investigator. Any untoward (unfavorable and unintended) change from baseline in a protocol-specific parameter or question response that is clinically relevant, in the opinion of the Investigator, is to be reported as an AE. These clinically relevant changes will be reported regardless of causality.

#### 13.1.1. Definition of an Adverse Event

An adverse event (AE) is defined as any untoward medical occurrence in a subject taking part in the clinical study, and which does not necessarily require a causal relationship with the investigational product and/or a clinical trial procedure.

An AE can be any unfavourable and unintended sign (including an abnormal laboratory value), symptom, or disease temporally associated with the use of the investigational product, whether or not related to this product.

When an AE has a likely or very likely causal relationship with the investigational product and/or a clinical trial procedure, it is named undesirable effect or related AE.

#### 13.1.2. Local tolerability signs and symptoms (only applicable for cosmetic safety studies)

In cosmetic studies, local skin tolerability includes some expected functional and/or physical signs on the application area, observed by the Investigator or reported by the

Protocol Version: 01

This document contains confidential, proprietary information.

Protocol GLI.04.US.SL.023

CONFIDENTIAL

subjects. Those signs are collected in the final report based on scales or a diary. If the severity of a local skin tolerability sign or symptom, is such that the product application is permanently discontinued and/or a corrective concomitant treatment (except moisturizer or emollient) is prescribed, it is recorded as an undesirable effect (related AE).

#### 13.1.3. Definition of a Serious Adverse Event (SAE) and serious undesirable effect/related SAE

A serious adverse event (SAE) involves a serious injury that is life threatening, results in permanent impairment of a body function or permanent damage to a body structure or necessitates medical or surgical intervention to preclude permanent impairment of a body function or permanent damage to a body structure, requires inpatient hospitalization or prolongation of an existing hospitalization.

##### Notes:

The term “immediate vital risk” refers to an event in which the subject was at risk of death at the time of the event; it does not refer to an event that hypothetically might have caused death if it was more severe.

Inpatient hospitalization is considered to have occurred if the subject has had to stay for a night at the hospital. Hospitalization solely for the purpose of a diagnostic test (even if related to an AE), elective hospitalization for an intervention that was already planned before subject enrolment in the clinical trial, admission to a day-care facility, social admission (e.g., if the subject has no place to sleep), or administrative admission (e.g., for a yearly examination) should not be considered as a SAE.

A serious undesirable effect/related SAE is defined as any SAE which the Investigator classifies as having a reasonable possibility for a causal relationship with the investigational product and/or the clinical trial procedure.

## 13.2 Severity Assessment

For all AEs occurring during the clinical trial, the Investigator is to classify and report the intensity of AEs using the following definitions as a guideline:

- Mild: awareness of signs and symptoms, but easily tolerated
- Moderate: discomfort, enough to cause interference with usual activity
- Severe: incapacitating, with inability to work or perform usual activity.

## 13.3 Causality Assessment

The Investigator is to assess the causal relationship (causality) between an adverse event and the investigational product and/or the clinical trial procedure according to the following definitions

Protocol Version: 01

This document contains confidential, proprietary information.

Protocol GLI.04.US.SL.023

CONFIDENTIAL

(Decision of 25 November 2013 on Guideline on Annex I to Regulation (EC) No 1223/2009 (2013/674/EU) – Causality assessment of undesirable effect caused by cosmetic products):

- Very likely
- Likely
- Unlikely
- Excluded

Medical judgment should be used to determine the relationship, considering all relevant factors including the pattern of reaction, temporal relationships, positive de-challenge or re-challenge, relevant medical history, and confounding factors such as co-medication or concurrent diseases.

